8.3.4 Blood collection

The amount of blood collected amounts to max 22 ml per visit (see table 5).

Table 5. Maximum quantities of blood collected at visits

Table 3. Maximum quantities of	blood collected at v	713113				1			1	
			v1	v2	v3	v4	v5	v6	v7	
			Screening	Wk0	Wk4	Wk8	Wk10	Wk12	Wk14	
	Tube	ml								
Chemistry	Serum tube 1	8	8	8	8	8				32
P1NP				*		*				0
Anti-HB titer	Serum tube 2	3	*					3	3	6
Serum LPS binding protein (LBP) and Cytokines	Serum tube 3	4		4		4			4	12
Cytokines				**		**				0
Serum LPS binding protein (LBP)				**		**				0
Glucose	NAF bloed	2	2	2	2	2				8
Hematology and CTX	EDTA plasma tube 1	4	4	4	4	4				16
Hematology			***	***	***	***				0
CTX (beta crosslabs)				***		***				0
OPN and BDNF	EDTA plasma tube 2	4		4	4	4				12
Plasma levels of OPN				****	****	****				0
OPTIONAL BDNF				****		****				0
Total			14	22	18	22	0	3	7	86

^{*} Part of serum tube 1, ** Part of serum tube 2, *** Part of EDTA plasma tube 1, **** Part of EDTA plasma tube 2

Blood tubes for clinical chemistry and hematology, glucose, P1NP and CTX-1 will be sent to a routine lab for analysis after drawing. Blood for the other analysis in serum will be collected and centrifuged after clotting. The serum will be frozen in aliquots of 200µl and one rest volume.

Blood drawn for plasma will be centrifuged and the plasma will stored in aliquots of 200µl for the analysis of OPN and BDNF.

8.3.5 Fecal collection

Subjects are asked to collect spot fecal samples within 24h before visits 2, 4 and 7, resulting in 3 fecal spot samples. The maximum time window for the fecal samples is 48h before the visit. All material and instructions to collect a spot fecal sample will be provided to the subjects. Subjects are asked to collect their stool using the Fecesvanger (picture below).

Subjects need to collect approximately 3 times 1 - 2 grams of stool. This will be stored for potential exploratory analyses related to changes in fecal microbiota composition and/or functionality.

A collection vial with spoon will be provided to the subjects, to collect the spot sample. The rest of the stool is flushed away. Subsequently, the stool sample needs to be frozen at -20°C in the subject's home freezer. For this, an envelope and materials for transport will be provided to prevent the sample from thawing during transport. Also reserve materials will be provided, in case not enough material can be collected during a first attempt.

In relation to the collected sample, consistency must be scored by the participant, by means of the 7-point Bristol Stool Scale (see below).

8.3.6 Questionnaires

Subjects will receive weekly questionnaires in which symptoms related to upper or lower respiratory infections will be recorded. These questionnaires will be completed online, via subject's own smartphone or computer/laptop.

8.4 Withdrawal of individual subjects

Subjects can leave the study at any time for any reason if they wish to do so without any consequences. The investigator can decide to withdraw a subject from the study for urgent medical reasons.

8.5 Replacement of individual subjects after withdrawal

If subjects withdraw before visit 2, subjects will be replaced. Subjects not completing the study for any reason will be considered as drop-outs. Drop-out rate should not exceed 25% of enrolled subjects, a minimum of 105 subjects should complete the trial. Only when the drop-out rate exceeds 25%, drop-outs will be replaced to achieve the minimum number of subjects to complete the trial.

8.6 Follow-up of subjects withdrawn from treatment

After possible withdrawal, no follow-up of participants will take place, except in cases of withdrawal for medical reasons.

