4.4 Sample size calculation

Sample size calculation was based on a publication by Albers et al. (Albers et al. 2003). In this study (with another nutritional intervention), seroconversion after hepatitis B vaccination in the placebo group was 33%, and it was 63% in the active group. For the present study, we assumed seroconversion of 25% in the placebo group. To be able to detect a doubling of seroconversion (to 50%) in the active group, a sample size of 58 subjects per group was calculated (Sample Size Calculator (clincalc.com)), with an alpha of 0.05 and a power of 0.8. Taking into account a drop-out rate of ~15%, we propose to include 70 subjects per group.

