10 STATISTICAL ANALYSIS

A detailed Statistical Analysis Plan (SAP) will be prepared and signed-off by an independent statistician, ultimately before database lock.

Descriptive information: all parameters studied will be described as mean and standard deviation when normal distribution has been ascertained. When the data are not normally distributed, descriptive values will be represented by median and interquartile range. In all cases the number of observations per parameter will be provided.

Throughout the study a p-value of lower than 0.05 will be considered to detect a statistically relevant difference, applying two-sided testing.

In the SAP, the intention-to-treat (ITT) population and the per protocol (PP) population will be defined. In a blind data review meeting the criteria for excluding specific subjects from the PP population will be applied.

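### Section 8.6 ends follow-up after any non-medical withdrawal and gives no route to a week-14 titre for subjects who stop the product but would still attend

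*Protocol*

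**What the plan says.** Protocol section 8.6 is headed as dealing with subjects withdrawn from treatment, and its whole content is: "After possible withdrawal, no follow-up of participants will take place, except in cases of withdrawal for medical reasons". It does not say what the follow-up after a medical withdrawal collects.

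Section 8.4 speaks only of leaving, or being withdrawn from, the study. Section 8.5 adds: "Subjects not completing the study for any reason will be considered as drop-outs". It then sets the tolerance: "Drop-out rate should not exceed 25% of enrolled subjects, a minimum of 105 subjects should complete the trial". Replacement follows only beyond that point: "Only when the drop-out rate exceeds 25%, drop-outs will be replaced to achieve the minimum number of subjects to complete the trial".

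The sample size in section 4.4 allows for less: "Taking into account a drop-out rate of ~15%, we propose to include 70 subjects per group".

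The primary endpoint (section 8.1.1) is one measurement, the anti-hepatitis B titre at V7 in week 14. On populations, section 10 says that in the SAP "the intention-to-treat (ITT) population and the per protocol (PP) population will be defined". Section 10.1 names Fisher's exact test on responders and non-responders.

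**The concern.** The sections on withdrawal do not distinguish a subject who stops taking the product from one who leaves the study. Read with its heading, section 8.6 lets a site close the file on someone who is tired of the sachets but would still come for a blood draw. That subject's primary outcome is then missing because the protocol did not ask for it, not because it was unobtainable.

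A later SAP can choose how to treat a missing V7 titre. It cannot recover a sample that was never taken, so this matter is settled in the protocol. The medical exception also makes follow-up depend on the reason for stopping, which arises after randomisation and could differ between arms. The protocol does not show that it will differ.

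What is at stake is how far an all-randomised comparison of responders rests on data rather than on assumed outcomes.

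**Working it through.** **Inputs.** Placebo rate: "For the present study, we assumed seroconversion of 25% in the placebo group". Active rate and evaluable number: "To be able to detect a doubling of seroconversion (to 50%) in the active group, a sample size of 58 subjects per group was calculated". Two-sided alpha 0.05 and power 0.80 (sections 4.4 and 10). 70 per group, 140 in all. Drop-out about 15% planned and 25% tolerated. First vaccination at week 8 (sections 3 and 7.6). Entry titre at most 4 IU/L and no prior vaccination or infection (sections 4.2 and 4.3).

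**The plan's own figure.** With pooled variance and no continuity correction, n = [1.960 × √(2 × 0.375 × 0.625) + 0.842 × √(0.25 × 0.75 + 0.50 × 0.50)]² / 0.25² = [1.342 + 0.557]² / 0.0625, which rounds up to 58 per group, as stated. Then 58 / 0.85 = 68.2, rounded up to 69, against the 70 chosen. The 105 completers are 140 × 0.75.

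**Missing titres.** 0.15 × 140 = 21 as planned; 0.25 × 140 = 35 at the tolerated limit. The limit is not a hard cap: above it drop-outs are replaced, so the number randomised but lost could be higher.

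**Range for the all-randomised difference.** Let m be the share lost, taken as equal in both arms, and e the share of those losses that occur before week 8. Early leavers are unvaccinated with an entry titre of at most 4 IU/L, so they count as non-responders. Outcomes of later leavers are unknown. If completers show 25% v 50%:

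- centre = (0.50 − 0.25) × (1 − m)
- half-width = m × (1 − e)

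| m | e | centre | half-width | range (points) |
|---|---|---|---|---|
| 0.25 | 0.5 | 0.1875 | 0.125 | +6 to +31 |
| 0.15 | 0.5 | 0.2125 | 0.075 | +14 to +29 |
| 0.25 | 1 | 0.1875 | 0 | +19 |
| 0.25 | 0 | 0.1875 | 0.25 | −6 to +44 |
| 0.15 | 0 | 0.2125 | 0.15 | +6 to +36 |

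The documents do not give e; 0.5 is an assumption, and 0 and 1 are its extremes. The ends of each range need every late leaver in one arm to respond and none in the other, so they are limits and not predictions. At 25% loss the sign can reverse only if m × (1 − e) exceeds 0.1875, that is, if more than 0.1875 / 0.25 = 75% of losses come after week 8. At 15% loss it cannot reverse, because 0.2125 exceeds 0.15.

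**The case against.** The strongest reply is that section 8.6 need not bar anything useful. Section 8.4 is about leaving the study, leftover sachets are counted for compliance (section 6.8), and PP exclusions are applied at a blind review (section 10). All of this fits poor compliers staying in the study and dropping out of the PP population only. This stands in part. That stopping the sachets amounts to leaving the study is something a reader might infer from the heading of 8.6, but no text says so. What remains is that the sections are ambiguous and offer no route for such a subject.

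Four further inferences should be resisted.

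- **That an ITT primary analysis is promised and will have no data.** Section 10 says only that the two populations will be defined in the SAP, which is not shown and may set a rule for missing titres. Medical withdrawals are followed in some form, and a subject who leaves after V6 already has a week-12 titre.
- **That a quarter of subjects will be lost.** 25% is the tolerated limit; about 15% is planned and already in the sample size. That allowance protects the number of completers, however, not the comparison of all randomised subjects.
- **That the effect could plausibly reverse.** The −6 to +44 range treats every loss as if it came after vaccination started. Anyone leaving in the first 8 of 14 weeks is almost certainly a non-responder.
- **That the fix would restore power to 83%.** With 70 per arm, exact Fisher power is 83% with complete data at the planned rates, 73% if 15% count as non-responders and 63% if 25% do. The gap is not the cost of section 8.6. Subjects who stop before vaccination, if not then vaccinated, would still be non-responders when sampled, early stoppers of active product may lose any effect, and some will refuse further samples.

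**Conclusion.** The point holds as a weakness in data collection. Section 8.6 ends follow-up after non-medical withdrawal, leaves the content of medical follow-up unstated, and has no path for a subject off product but willing to attend. Any ITT comparison of V7 responders could therefore depend on assumed outcomes for about 21 of 140 subjects at the planned loss and 35 at the tolerated limit, chiefly for those who leave from week 8 onward.

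At 25% loss, half of it before week 8, the all-randomised difference could lie between about +6 and +31 points. This rests on equal loss in both arms, completers at 25% v 50%, and the assumed timing. That range is 25 points wide, as wide as the effect the trial was sized to detect. The gain in power from a change cannot be stated without assumptions on timing, consent and dilution. The change is worth making because it is cheap and no later analysis can replace it.

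**What to change.** In sections 8.4 to 8.6, define stopping the study product and withdrawing from the study as separate events. State that every randomised subject who has not withdrawn consent, whatever the reason for stopping, is asked for the V6 and V7 blood samples and the weekly questionnaires, and is analysed as randomised in the ITT population. State that follow-up after medical withdrawal includes these same samples. Leave all decisions on product and vaccine unchanged.

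The cost is an amendment and a small added burden for a few subjects. Both draws are already scheduled, at 3 ml and 7 ml (section 8.3.4, Table 5). The payment steps in section 11.5 already cover them: 620 − 500 = 120 euro for V6 and 750 − 620 = 130 euro for V7. Subjects who withdraw consent remain missing, so the change reduces the loss without removing it.

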8.7 Premature termination of the study

The study will only be terminated if an acute serious adverse event (SAE) occurs which in the opinion of the responsible medical investigator may be related to the test product. In case of premature termination of the study by the investigators, the subjects will be informed of the reason for termination and will be paid pro rata for the part of the study that has already been performed.

9 SAFETY REPORTING

9.1 Temporary halt for reasons of subject safety

In accordance with section 10, subsection 4, of the WMO, the sponsor will suspend the study if there is sufficient ground that continuation of the study will jeopardise subject health or safety. The sponsor will notify the METC without undue delay of a temporary halt including the reason for such an action. The study will be suspended pending a further positive decision by the METC. The investigator will take care that all subjects are kept informed.

9.2 AEs and SAEs

9.2.1 Adverse events (AEs)

Adverse events are defined as any undesirable experience occurring to a subject during the study, whether or not considered related to [the investigational product / trial procedure/ the experimental intervention]. All adverse events reported spontaneously by the subject or observed by the investigator or his staff will be recorded.

9.2.2 Serious adverse events (SAEs)

A serious adverse event is any untoward medical occurrence or effect that

- results in death;
- is life threatening (at the time of the event);
- requires hospitalisation or prolongation of existing inpatients' hospitalisation;
- results in persistent or significant disability or incapacity;
- is a congenital anomaly or birth defect; or
- any other important medical event that did not result in any of the outcomes listed above due to medical or surgical intervention but could have been based upon appropriate judgement by the investigator.

An elective hospital admission will not be considered as a serious adverse event.

The investigator will report all SAEs to the sponsor without undue delay after obtaining knowledge of the events. The sponsor will report the SAEs through the web portal *ToetsingOnline* to the METC that approved the protocol, within 7 days of first knowledge for SAEs that result in death or are life threatening followed by a period of maximum of 8 days to complete the initial preliminary report. All

other SAEs will be reported within a period of maximum 15 days after the sponsor has first knowledge of the serious adverse events.

9.3 Follow-up of adverse events

All AEs will be followed until they have abated, or until a stable situation has been reached. Depending on the event, follow up may require additional tests or medical procedures as indicated, and/or referral to the general physician or a medical specialist.

SAEs need to be reported till end of study within the Netherlands, as defined in the protocol.

10 STATISTICAL ANALYSIS

A detailed Statistical Analysis Plan (SAP) will be prepared and signed-off by an independent statistician, ultimately before database lock.

Descriptive information: all parameters studied will be described as mean and standard deviation when normal distribution has been ascertained. When the data are not normally distributed, descriptive values will be represented by median and interquartile range. In all cases the number of observations per parameter will be provided.

Throughout the study a p-value of lower than 0.05 will be considered to detect a statistically relevant difference, applying two-sided testing.

In the SAP, the intention-to-treat (ITT) population and the per protocol (PP) population will be defined. In a blind data review meeting the criteria for excluding specific subjects from the PP population will be applied.

10.1 Primary study parameter(s)

Subjects will be classified as responders and non-responders for antibody production. Responders are subjects with an anti HB antibody titer of ≥10 IU/L, non-responders have a titer < 10 IU/L. The difference in number of responders for hepatitis B-specific antibody production will be analyzed by Fisher's exact test.

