8.2 Randomisation, blinding and treatment allocation

To ensure blinding of the NIZO study team, an independent person in the AFI study team will be responsible for assigning a random 5-digit number code to the products. The number code is printed on the label of each carton box. Per treatment 3 different, 5 digits, codes will be used. The NIZO and EBMR teams, laboratory personnel and participants will be unaware of the coding until all data analyses are finished and until after the blind data review meeting. Only in a case of emergency possibly related to treatment, the Principal Investigator can request the independent party to open a sealed de-blinding envelope containing information to check the type of treatment of (a) particular subject(s) without disclosure of the other treatments.

Allocation will be stratified for gender and age.

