10.2 Secondary study parameter(s)

The data will be analyzed with Linear Mixed Models (LMMs). LMMs model data from repeated measurements (where measurements from the same individual cannot be assumed to be independent) by including a separate model intercept for each longitudinal study unit (i.e. individual). Treatment group and timepoint will be included as fixed effects, while the study participant will be included as a random effect. Additionally, covariates will also be included as fixed effects: study location, age, gender, baseline value of the outcome parameter. An interaction term

between the effect of time and the effect of treatment groups will also be included in order to assess whether the outcome in question is differentially affected by the Lacprodan® OPN-10 intervention compared to placebo.

Model goodness-of-fit will be assessed and model assumptions (linearity, homoscedasticity, linearity of residuals, non-collinearity of parameters) will be checked.

In cases where the outcome distribution shows departure from normality, the outcome parameter of the LMM will be log-transformed.

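### The primary Fisher's exact test falls short of the planned 80% power at the planned sample size, mainly through its own conservatism, and it also leaves the randomisation strata unused

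*Protocol*

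**What the plan says.** Section 8.2 of the protocol: "Allocation will be stratified for gender and age". It gives no age bands.

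Section 10.1 on the primary endpoint: "The difference in number of responders for hepatitis B-specific antibody production will be analyzed by" Fisher's exact test. It names no strata or covariates.

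Section 10.2, on the linear mixed models for the secondary parameters: "covariates will also be included as fixed effects: study location, age, gender, baseline value of the outcome parameter".

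Section 4.4 on sample size: "we assumed seroconversion of 25% in the placebo group". The target difference follows: "To be able to detect a doubling of seroconversion (to 50%) in the active group". The result is 58 per group, "with an alpha of 0.05 and a power of 0.8", raised to 70 per group for dropout of about 15%. The calculation is attributed to an online calculator, and the formula is not named.

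Section 10 sets the significance rule: "a p-value of lower than 0.05 will be considered to detect a statistically relevant difference, applying two-sided testing".

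Section 8.5 sets a floor of 105 completers.

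**The concern.** The trial has one primary endpoint and one confirmatory test, and two features of that test do not fit the rest of the plan.

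First, the sample size comes from a formula for a test less conservative than the one that will be run. If Fisher's test has materially less power than that formula assumes, the 80% in section 4.4 is not what the trial delivers.

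Second, gender and age are treated as important enough to balance at allocation and to adjust for in the secondary models, but the primary test ignores them. When prognostic factors are balanced by design, an unstratified test still counts the variation between strata as noise, and some efficiency is lost.

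At stake is the chance of missing a real doubling of the response rate.

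**Working it through.** **Inputs.** Response 25% (placebo) and 50% (active), alpha 0.05, power 0.80, 58 evaluable and 70 enrolled per group, dropout about 15% (section 4.4). Two-sided testing (section 10). At least 105 completers (section 8.5).

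**Step 1: reproduce the plan's figure.** Pooled-variance normal approximation, no continuity correction, with mean rate 0.375:

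n = [1.960 × √(2 × 0.375 × 0.625) + 0.842 × √(0.25 × 0.75 + 0.5 × 0.5)]² / 0.25²

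= [1.960 × 0.6847 + 0.842 × 0.6614]² / 0.0625 = (1.342 + 0.557)² / 0.0625 ≈ 57.7, rounded up to **58**.

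This matches section 4.4. The continuity-corrected version gives 66. Dropout: 58 / 0.85 = 68.2, so 69, close to the 70 stated. Expected completers are 70 × 0.85 = 59.5 per group. The floor is 105 / 2 = 52.5 per group.

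**Step 2: power of the test named in 10.1.** The two binomials are enumerated in full, and the probabilities of all tables with p < 0.05 are added up. Pearson's unstratified chi-square test without correction is the comparator, because it separates Fisher's conservatism from the effect of the strata.

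| Per arm | Fisher | Pearson |
|---|---|---|
| 52 | 70.3% | 77.2% |
| 58 | 74.3% | 79.9% |
| 60 | 76.0% | 81.8% |
| 65 | 80.9% | 85.4% |
| 70 | 83.1% | 87.0% |

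Fisher's test first passes 80% at 64 per arm (80.2%). Its true size at 58 per arm is 3.2% for a common rate of 25% and 3.1% for 37.5%. Pearson's is 5.2% and 4.8%.

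The gap at 58 per arm is 79.9 − 74.3 = **5.6 points**, and no strata are involved in it.

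**Step 3: the extra cost of ignoring the strata.** This needs assumptions that the protocol does not supply: four near-equal strata (gender by two age bands), arms balanced within strata, marginal rates held at 25% and 50%, and the same prognostic odds ratio for each factor. Simulated power at 58 per arm (40,000 runs per setting), with the Cochran-Mantel-Haenszel (CMH) test uncorrected:

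| Odds ratio per factor | Fisher | Pearson | CMH | CMH − Pearson |
|---|---|---|---|---|
| 1 | 74.3% | 80.0% | 79.9% | about 0 |
| 1.5 | 74.4% | 79.9% | 80.4% | 0.5 |
| 2 | 74.5% | 80.2% | 82.0% | 1.8 |
| 3 | 75.1% | 81.0% | 84.6% | 3.6 |
| 4 | 76.2% | 82.0% | 86.8% | 4.8 |

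The last column is the cost of leaving out the strata. The total Fisher-to-CMH gap runs from 79.9 − 74.3 = 5.6 to 86.8 − 76.2 = 10.6 points, and at odds ratios up to 2 most of it is Fisher's discreteness.

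Under the null, at a common rate of 37.5%, uncorrected CMH has a size of 4.8% to 5.1% at 58 per arm across these settings. Fisher's falls from 3.1% to 1.8% as the factors become more prognostic.

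**Step 4: does the form of CMH matter?** With a continuity correction and no prognostic effect, CMH has about 74% power at 58 per arm, the same as Fisher's test. Stratifying with that correction would then gain nothing.

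**The case against.** **Validity.** A reader might infer that an unstratified test after stratified allocation is invalid. It is not: the true size stays below 5% in every setting examined. The issue is efficiency only.

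**Cause.** A reader might also infer that ignoring gender and age is what costs the power, at 5 to 9 points. The figures do not support that. With no prognostic effect the gap to CMH is already 5.6 points, and plain Pearson closes it without any stratification.

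**Evidence that the factors matter.** Section 1.3 reports lower response above 40 years under standard schedules. All subjects here are at least 60 and receive an accelerated schedule, so this shows no age gradient within the trial population. Nothing in the protocol says that gender predicts response. This objection stands, which is why the stratification component is given only as a range under assumed odds ratios.

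**Enrolment of 70 per arm.** With no dropout Fisher's test would have 83.1% power. But section 4.4 itself expects about 15% dropout, leaving 59.5 per arm, where power is about 76%.

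**Left to the SAP.** Section 10 promises a detailed SAP, and a supportive adjusted estimate can properly wait for it, so its absence from 10.1 is not a defect. The choice of primary test is different: 10.1 fixes it, and an SAP would have to depart from the protocol to change it.

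**Conclusion.** The point holds as a mismatch between the sample size calculation and the planned test, with unused strata as a smaller second component. At the protocol's own rates and alpha, Fisher's test delivers 74.3% power at the calculated 58 per arm, about 76% at the expected number of completers and about 70% near the 105-completer floor, against the stated 80%. These figures need no assumption beyond those in section 4.4.

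About 5.6 points of the loss at 58 per arm are Fisher's discreteness. Leaving out gender and age adds about 0 to 2 points for odds ratios up to 2 per factor and about 4 at 3. That part rests on assumed odds ratios and on four near-equal strata.

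The planned test remains valid. The change is worth making because it is cheap and restores the stated power, not because the analysis would mislead.

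**What to change.** In section 10.1, make the primary test a Cochran-Mantel-Haenszel test without continuity correction over the gender-by-age strata used at randomisation. Report the Mantel-Haenszel risk difference with its 95% CI, and keep Fisher's exact test as a sensitivity analysis. State explicitly that no continuity correction is applied, since the corrected version can lose the whole gain. The age bands used for allocation must be written down so that the strata are defined.

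This gives about 80% power at 58 per arm with no prognostic effect, and more if the factors matter. The cost is a short change to 10.1, carried into the SAP. Gender and age are already needed for allocation, and recruitment is unaffected. The drawback is an asymptotic rather than an exact test, so stratum sizes should be checked once the age bands are known.

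If Fisher's test is kept as primary, restate the power in section 4.4 as about 74% at 58 per arm (about 76% at 60). Holding 80% with Fisher's test would instead take about 65 evaluable per arm, or 65 / 0.85 = 76.5, so 77 enrolled per arm.
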